## 7.2 Analyses

Diclofenac concentrations will be measured in serum samples collected from each subject. Blood samples (approximately 5 mL (1 tsp)) will be collected during Study Session 1 prior to dosing and then at 1 h, 2 h, 3 h, 4 h, 5 h, 6 h, 7 h, 8 h, 9 h, 10 h, 24 h, 27 h, 30 h, 32 h and 51 h post-patch application. Blood samples (approximately 5 mL (1 tsp)) will be collected during Study Session 2 prior to dosing and then at 1 h, 2 h, 3 h, 4 h, 5 h, 6 h, 7 h, 23 h, 26 h, 29 h, 31 h and 47 h post-solution application. After the PK study, TS study will be conducted at 10 h [patches] and 6 h [solution] (skin drug uptake/absorption), 27 h [patches] and 23 h [solution] (skin drug clearance), and 51 h [patches] and 47 h [solution] (skin drug clearance) post product application. Non compartmental analyses (NCA) will be conducted to estimate the PK parameters such as: maximum serum concentration  $(C_{max})$ ; apparent elimination rate constant (k); apparent half-life (t1/2), calculated as 0.693/k; AUC0-last of the serum concentration-time determined by the linear trapezoidal method; and AUC value extrapolated to infinity (AUCinf), calculated as the sum of AUC0-last and the area extrapolated to infinity: AUCinf = AUC0-last + Clast/k where Clast would be the last guantifiable concentration. All NCA analyses will be conducted using Phoenix® WinNonlin® 6.4 (Pharsight, a Certara Company, CA).

## 7.3 Final Analysis Plan

An objective of this study is to determine PK parameters ( $C_{max}$ , AUC and ratio of SC drug concentration during uptake and clearance) of diclofenac in healthy adults and TS data after using Flector® (diclofenac epolamine 1.3% patch) and Pennsaid® (2% diclofenac sodium topical solution) for the purpose of IVIVC by collecting data over two separate application periods.

Analysis of variance (ANOVA) followed by post-hoc Bonferroni test will be used for comparing the differences in the means of the PK parameters and significant differences will be declared at p<0.05. The statistical comparisons will be conducted as follow:

If diclofenac PK concentrations are found to be non-normally distributed, then we will examine Box-Cox transformations (e.g., log, square-root, etc.) that can achieve normality. If no transformation can achieve normality, then will use permutation tests to compute empirical *p*-values, and will use the bootstrap to compute standard errors and confidence intervals that account for within-person correlation.

IVIVC will be conducted comparing PK parameters and profiles to predicted PK parameters and profiles using IVPT and in vitro TS results. Multiple methods will be implemented to develop an IVIVC. The first method is to compare the steady state concentrations. The predicted steady state concentration using IVPT data will employ the following formula:

$$C_{ss} = \frac{J_{ss} * A}{CL}$$

The second method will compare the PK profiles of the clinical and IVPT study by predicting diclofenac concentrations at each time point in the IVPT study and comparing it to the clinical PK profile. The third method will be to determine and compare residual patch analysis between in vitro and in vivo.

In terms of developing an IVIVC for the TS study a comparison will be made between in vitro and in vivo uptake (absorption) and clearance diclofenac amounts. The second method is to compare the clearance to uptake diclofenac amount ratio between in vitro and in vivo.

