#### Flector® patch and Pennsaid® topical solution

# **3 OBJECTIVES**

#### 3.1 Study Objectives

1) Generate human PK data for the purpose of establishing an IVIVC model by collecting data following the application of two diclofenac formulations: Flector® 1.3% diclofenac epolamine patches and Pennsaid® 2% diclofenac sodium topical solution.

2) Generate TS data for the purpose of establishing a fundamental IVIVC model by collecting skin concentration data following the application of two diclofenac formulations: Flector® 1.3% diclofenac epolamine patches and Pennsaid® 2% diclofenac sodium topical solution.

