# 7 PHARMACOKINETICS AND STATISTICAL CONSIDERATIONS

## 7.1 Study Hypothesis

#### TS and PK

The tested diclofenac products are non-bioequivalent hence, we will test the null hypothesis ( $H_0$ ) that the mean clearance/uptake diclofenac amount ratio, and the PK parameters ( $C_{max}$  and AUC) between these products are different (i.e., outside the 80–125% range).

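### Section 7.1 sets a null of between-product ratios outside 80–125%, but the ANOVA of equal means in section 7.3 does not test it

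*Combined protocol and SAP*

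**What the plan says.** Section 7.1 opens with "The tested diclofenac products are non-bioequivalent hence, we will test the null hypothesis". It defines that null as the clearance/uptake amount ratio, Cmax and AUC being such that they "between these products are different (i.e., outside the 80–125% range".

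Section 7.3 gives the test: "Analysis of variance (ANOVA) followed by post-hoc Bonferroni test will be used for comparing the differences in the means of the PK parameters", at p<0.05. It counts the stratum corneum ratio among the PK parameters, so the ANOVA covers all three quantities named in 7.1. The sentence "The statistical comparisons will be conducted as follow" ends in a colon, and no list follows in the available text.

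What follows is a fallback for non-normal data: "If diclofenac PK concentrations are found to be non-normally distributed, then we will examine Box-Cox transformations (e.g., log, square-root, etc.) that can achieve normality". If that fails, the plan uses permutation p-values and "will use the bootstrap to compute standard errors and confidence intervals that account for within-person correlation". No confidence level and no acceptance limits are attached.

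Section 7.1 names only AUC. Section 7.2 defines two: AUC to the last quantifiable sample "of the serum concentration-time determined by the linear trapezoidal method; and AUC value extrapolated to infinity".

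**The concern.** The two sections pose opposite questions. Under 7.1, non-equivalence is the null, and rejecting it supports a ratio within the limits. Under 7.3, equality is the null, and rejecting it supports a difference. A small p-value from 7.3 does not place the ratio outside 80–125%, and a large one does not place it inside.

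The 7.1 wording has a further problem. It expects non-bioequivalence but makes it the null, so the expected finding could be supported only by failing to reject.

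What is at stake is the between-product conclusion: an ANOVA p-value could be reported as a verdict on 80–125% when it is not one.

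**Working it through.** **The two rules side by side**

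| | Section 7.1 | Section 7.3 |
|---|---|---|
| Null | ratio outside 80–125% | means equal |
| Rejection means | ratio inside the limits | products differ |
| Limits used | 80–125% | none |
| Criterion | none given | p<0.05 |

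The only other mention of these limits is in section 2.1, as background on the tape-stripping method. The remaining comparisons in 7.3 are in vitro against in vivo. The documents give no power or sample-size figure to reproduce.

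**Inputs.** n = 12, each subject receiving both products (Protocol Summary; section 4). Two-sided 0.05 (7.3; an F test has no direction). Limits 0.80 and 1.25 (7.1). Assumed, because the documents give none: log-normal data and within-subject CV from 10% to 40%.

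**Formulas.** SD of a paired log difference = √(2·ln(1+CV²)); SE = SD/√12; 11 degrees of freedom; t(0.975) = 2.201 and t(0.95) = 1.796.
- Equal-means rule: significant if |ln observed ratio| > 2.201·SE.
- Limits rule: the 90% CI is ln(observed ratio) ± 1.796·SE, compared with ln 0.80 = −0.223 and ln 1.25 = 0.223.

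**By hand, with the sample SD equal to its assumed value**
- CV 10%: SD = √(2·ln 1.01) = 0.141; SE = 0.0407. Significance needs an observed ratio above exp(2.201 × 0.0407) = 1.094. The 90% CI stays below 1.25 up to 1.25·exp(−1.796 × 0.0407) = 1.162. Any observed ratio from 1.094 to 1.162 is therefore significantly different and also within limits. At 1.12, t = 0.1133/0.0407 = 2.78, p = 0.018, and the 90% CI is 1.04 to 1.20.
- CV 30%: SD = √(2·ln 1.09) = 0.415; SE = 0.120. Significance needs a ratio above exp(2.201 × 0.120) = 1.30. A 90% CI wholly above 1.25 needs 1.25·exp(1.796 × 0.120) = 1.55. From 1.30 to 1.55 the test is significant but a ratio outside the limits has not been shown.

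**By simulation** (400,000 trials per cell, sample SD varying)

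| True ratio | CV | p<0.05 | p<0.05 and 90% CI inside | 90% CI wholly outside |
|---|---|---|---|---|
| 1.12 | 10% | 72% | 53% | about 0% |
| 1.12 | 15% | 40% | 9% | <0.1% |
| 1.12 | 20% | 25% | 1% | 0.2% |
| 1.12 | 30% | 14% | <0.1% | 0.6% |
| 1.12 | 40% | 10% | about 0% | 1% |
| 1.5 | 20% | 99.5% | about 0% | 68% |
| 1.5 | 30% | 87% | about 0% | 41% |
| 1.5 | 40% | 65% | about 0% | 29% |
| 2.0 | 30% | 99.9% | 0% | 98% |
| 2.0 | 40% | 98% | 0% | 88% |

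**Non-significance read as equivalence.** At a true ratio of 1.25, on the edge of the 7.1 null, p is 0.05 or more in 29%, 60% and 75% of trials at CV 20%, 30% and 40%. The CI rule concludes equivalence there in 5.0%, 3.4% and 1.1%.

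**Bonferroni.** Two products give one contrast per endpoint, so a post-hoc correction changes nothing unless it runs across endpoints, which 7.3 does not say. Counting Cmax, one AUC and the ratio at two clearance times gives four endpoints and a threshold of 0.05/4 = 0.0125. At a true ratio of 1.12 and CV 10%, that threshold is met in 46% of trials, and in 31% it is met with the 90% CI inside. The mismatch remains.

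**Scale.** The default in 7.3 is untransformed. With between-subject CV assumed at 30–70%, p<0.05 occurs in 56–68% at ratio 1.12, CV 10%, and in 71–82% at ratio 1.5, CV 30%.

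**The case against.** Four points deserve weight.

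- **Text may be missing.** The colon with nothing after it is where a decision rule could have stood, and the text was machine-read. The conclusion is therefore limited to the available text, and the colon is not counted as a fault. But the stated rule, a difference at p<0.05, is complete in itself and already conflicts with 7.1.
- **The consequence is narrow.** The objectives are of the kind "Generate human PK data for the purpose of establishing an IVIVC model"; the IVIVC methods use no between-product p-value, and no sample size rests on this test. This stands, and it limits the finding to the between-product conclusion.
- **The numbers rest on assumed CVs.** A significant p-value with the CI inside the limits is common only at low CV: 53% at 10%, 9% at 15%, 1% at 20%. At a true ratio of 1.5 a significant ANOVA points the right way and only the strength of proof falls short. At 2.0 the rules mostly agree. The PK ratios may be that far from 1: the applied loads are 4 × 180 = 720 mg of epolamine salt and 4 g × 20 mg/g = 80 mg of sodium salt, although load does not fix exposure. The clearance/uptake ratio is formed within product and may lie nearer 1, but the documents do not show this. The logical mismatch needs none of these values.
- **Bonferroni may have work to do.** A product-by-time ANOVA of the clearance/uptake ratio would have several contrasts. That is a possible reading, but 7.3 does not specify such a model.

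ANOVA is not itself the fault: its residual variance could supply the interval. The missing part is the step that compares that interval with the limits.

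**Conclusion.** The concern holds. As written, sections 7.1 and 7.3 test opposite nulls, and no procedure in the available text, fallback included, applies 80–125%. The plan cannot answer its own stated hypothesis. This follows from the wording alone.

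The practical size depends on the true ratio and on a CV the documents do not give. It is large when the ratio is near 1 with low variability, or moderately outside the limits with ordinary variability. It is small when the ratio is about 2 or more. The IVIVC and descriptive results are unaffected. This should be fixed before analysis; it does not threaten the study's main purpose.

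**What to change.** Choose one.

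**(a) If only a difference is of interest.** Rewrite 7.1 as a null of no difference between products in Cmax, one named AUC and the clearance/uptake ratio. Remove the 80–125% range, say whether Bonferroni applies across endpoints, and state that the p-value is not a verdict on bioequivalence. Cost: a few sentences.

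**(b) If 80–125% is kept.**
- Log-transform a priori Cmax, one named AUC and the clearance/uptake ratio at each clearance time. AUC to the last quantifiable sample is one choice, with AUCinf supportive: planned sampling ends 41 h after removal for both products (51 − 10 and 47 − 6), though the last quantifiable sample may come earlier.
- Fit product with subject in the model. For tape stripping, average the two replicate sites per product and time, or nest them in subject. State how unquantifiable amounts are handled before taking logs, for example as left-censored, with half-limit substitution as a sensitivity analysis.
- Report the geometric mean ratio with its 90% CI: equivalent if within 80.00–125.00%, non-equivalent if wholly outside, otherwise inconclusive.
- An overall equivalence claim requires every endpoint and needs no adjustment. Endpoint-by-endpoint non-equivalence claims do need it: with four independent endpoints at the limit, the chance of a false claim is 1 − 0.95⁴ = 18.5%, and 97.5% CIs bring it to 4.9%.

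Cost of (b): SAP wording and a few lines of code, but many results may be inconclusive. At CV 20%, 30% and 40%:

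| True ratio | Inconclusive, unadjusted | Inconclusive, 97.5% CI for non-equivalence |
|---|---|---|
| 1.5 | 32%, 58.5%, 71% | 60%, 81%, 89% |
| 2.0 | <0.1%, 2%, 12% | 0.2%, 11%, 34% |

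Even at a true ratio of 1.0, a single endpoint meets equivalence in only 65%, 16% and 3%. That favours (a) unless equivalence is a real aim.

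Under either option, add one sentence noting that the patch is in Session 1 and the solution in Session 2 with no randomised order described, so the PK product effect cannot be separated from period. Tape stripping is not affected, since both products are in Session 3. Neither option needs new data or subjects.

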In 1998, the FDA issued draft guidance for the dermatopharmacokinetics (DPK) method to assess the bioequivalence of topical products for application to the skin. The approach required quantification of the total amount of drug in the stratum corneum (SC) as a function of time, akin to the typical concentration-time profiles of traditional PK studies using blood sampling. Tape-stripping, a technique that involves multiple applications and removal of individual pieces of tape to a formulation-treated area of the skin of a healthy human subject, is the biosampling method used in TS to remove layers of the SC in serial. The draft guidance was withdrawn in 2002 following the inconsistent results of two studies. The lack of agreement in the results prompted concern about both the reproducibility and the adequacy of this method to assess drugs whose target site is beyond the SC.

Considerable subsequent effort was directed at identification of problems/limitations of the original TS protocol and development of an improved procedure to generate reproducible data of much higher quality.

The end product of this research was a relatively straightforward method that examines only one uptake and one elimination time per formulation. This allows replicate sites to

7

be studied, and higher statistical power to be achieved with fewer volunteers. No tapes are discarded, but tapes are combined and extracted in groups to achieve high concentrations for analysis. The total amount of drug in the SC is measured for each site, and the ratios of these quantities for a reference listed drug (RLD) and test formulations can then be compared in the usual "80:125" area under the curve bioequivalence fashion. The method has been successively applied retrospectively to the comparison of retinoid gels and prospectively to the analysis of DPK data obtained for 3 econazole creams.

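### Section 7.3 lets a normality check and a Box-Cox search choose the analysis scale, so the log scale on which the 80–125% limits of section 7.1 are constant is permitted but not secured

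*Combined protocol and SAP*

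**What the plan says.** Section 7.1 (Study Hypothesis) covers the tape-stripping clearance/uptake ratio, Cmax and AUC. Its null hypothesis is that these "between these products are different (i.e., outside the 80–125% range". Section 2.1 describes the same framing for the tape-stripping method, where test-to-reference ratios are judged against 80:125 limits.

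Section 7.3 (Final Analysis Plan) states the analysis: "Analysis of variance (ANOVA) followed by post-hoc Bonferroni test will be used for comparing the differences in the means of the PK parameters". The threshold for calling a difference significant is p<0.05. The section then gives a rule for the scale in three steps:

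1. The untransformed scale is the default.
2. "If diclofenac PK concentrations are found to be non-normally distributed, then we will examine Box-Cox transformations". The candidates are "Box-Cox transformations (e.g., log, square-root, etc.) that can achieve normality".
3. If nothing achieves normality, permutation p-values are used, with bootstrap standard errors and "confidence intervals that account for within-person correlation".

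The documents do not name the normality test or its threshold. They nowhere fix the log scale for Cmax, AUC or the clearance/uptake ratio. They mention no geometric mean ratio, 90% confidence interval or two one-sided tests, and no way to turn a raw or square-root difference into a ratio.

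**The concern.** The hypothesis concerns a ratio, but the analysis compares means on whichever scale looks normal. The scale determines what is estimated: a difference of arithmetic means, a difference of mean square roots, or the log of a ratio of geometric means. Only the last can be compared with 80–125% without knowing the reference mean. A rule that reaches it only when a check on the study data happens to point there may leave section 7.1 without an answer on its own terms.

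The variable being checked is also unclear. The wording refers to concentrations, while the quantities compared are Cmax, AUC and the clearance/uptake ratio. For a within-subject comparison the relevant distribution is that of the paired differences or model residuals.

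At stake are a pre-specified estimand and, once an equivalence test is in place, its error rate and power.

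**Working it through.** The plan gives no CV, expected ratio, power or sample-size derivation, so it has no figure to reproduce. From the documents come the 80–125% limits (7.1), 12 subjects who each receive both products (section 4), and the scale rule (7.3). Assumed: lognormal data, the CVs shown, Shapiro-Wilk at 0.05, and a one-sided 5% equivalence test (90% interval).

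**Step 1: the limits on each scale.** Let μ be the reference mean.
- Log: ln 0.80 = −0.2231 and ln 1.25 = +0.2231, whatever μ is.
- Raw: −0.20μ and +0.25μ.
- Square root: √μ(√0.80 − 1) = −0.1056√μ and √μ(√1.25 − 1) = +0.1180√μ.

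| μ | Raw limits | Square-root limits | Log limits |
|---|---|---|---|
| 1 | −0.20 / +0.25 | −0.106 / +0.118 | ±0.2231 |
| 5 | −1.0 / +1.25 | −0.236 / +0.264 | ±0.2231 |
| 20 | −4 / +5 | −0.472 / +0.528 | ±0.2231 |
| 100 | −20 / +25 | −1.056 / +1.180 | ±0.2231 |

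Off the log scale the limits are asymmetric and move with a mean that must itself be estimated.

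**Step 2: which scale the rule would select.** There are two readings.

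*(a) The check is made on 12 Cmax or AUC values.* For lognormal samples with CV 30, 40, 50 and 60%, Shapiro-Wilk rejects in about 14%, 20%, 28% and 35%. The raw scale is therefore kept in about 86%, 80%, 72% and 65%. A second simulation set between- and within-subject CVs separately. Total CV is √[(1 + CVb²)(1 + CVw²) − 1], for example √(1.36 × 1.16 − 1) = 76% at 60/40. There, raw was kept in about 82–84% at between-subject CV 30%, 70–72% at 40% and 54–60% at 60%. In a further 9–29% of trials raw failed but square root passed.

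*(b) The check is made on pooled concentrations.* Session 1 gives 12 × 16 = 192 values over a rise and fall. With an assumed profile of that shape, Shapiro-Wilk rejected in all of 1,000 simulated datasets at each CV from 30% to 60%. The raw scale then drops out, the Box-Cox search sets the scale, and the check has said nothing about Cmax or AUC across subjects.

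The two readings exclude each other. Neither secures the log scale.

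**Step 3: consequence once an equivalence test is added.** These are simulated paired trials, n = 12. The raw and square-root intervals use limits set from the estimated reference mean. Fieller-type means testing T − 0.80R and T − 1.25R directly.

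| CV between/within (%) | True ratio | Log | Raw, estimated limits | Raw, Fieller-type | Square root |
|---|---|---|---|---|---|
| 30/15 | 1.25 | 4.8% | 7.2% | 4.7% | 5.8% |
| 30/20 | 1.25 | 5.0% | 7.3% | 4.9% | 5.9% |
| 50/20 | 1.25 | 5.0% | 7.9% | 4.5% | 6.2% |
| 40/30 | 1.25 | 3.4% | 4.4% | 3.0% | 4.0% |
| 60/30 | 1.25 | 3.5% | 4.8% | 3.1% | 4.2% |
| 60/40 | 1.25 | 1.0% | 1.6% | 0.9% | 1.2% |
| 30/15 | 0.80 | 5.2% | 4.2% | 5.1% | 4.6% |
| 30/20 | 0.80 | 5.2% | 4.2% | 5.2% | 4.7% |

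Entries are the rate of declaring equivalence at a limit, where 5% is nominal. At 50/20 and ratio 0.80 the raw rate is about 4.6%.

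Power at ratio 1 is about 54% raw against 66% log at 50/20, and 59% against 65% at 30/20. The gap nearly closes at 40/30 (14% against 16%).

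**The case against.** Several points on the other side stand.

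- **The plan allows the right scale.** Log is the first transformation named. Nothing says that the fitted Box-Cox power must be used, and in simulation the 95% interval for that power included log in about 97% of datasets. A sensible analyst may well choose log.
- **A reader might infer that the raw scale cannot test the range at all.** That goes too far. Fieller-type contrasts, or a bootstrap interval for a ratio, would test a ratio of arithmetic means, and the contrasts held about 5% or less. The plan names neither, but the problem is an unspecified step and not an impossible one.
- **A reader might infer that error is inflated in general.** It is not. The excess appears at ratio 1.25 with low within-subject CV, and only if the estimated reference mean is treated as fixed. It also presupposes an equivalence test. The plan has only a difference test at p<0.05, so these rates do not describe the analysis as written.
- **The reference to concentrations may be loose wording.** It follows directly on a sentence about PK parameters, and nothing says that time points are pooled.
- **A reader might infer that the main ANOVA ignores pairing, because within-person correlation appears only in the last fallback.** The design is declared a crossover, and section 7.3 does not say that subject is left out of the model. This is missing detail.
- **The consequence is limited.** Section 7.1 presumes the products non-bioequivalent. At a true ratio of 1.5 with CVs 50/20, the raw-scale rate of false equivalence is about 0.04%.

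What remains is that the scale is left to the data and the hypothesis needs one particular scale.

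**Conclusion.** The concern holds in a limited form. Section 7.3 states a rule that can place the analysis on a scale where the limits of section 7.1 are not constants, and it gives no route back to a ratio. That follows from the text and from step 1, with no distributional assumption.

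How often it would happen, and at what cost, rests on assumptions because the documents give no variability. For lognormal data and a check on Cmax or AUC, the raw scale would be kept in roughly two thirds to six sevenths of datasets at CV 60–30%. The cost in a later equivalence test ranges from about 2–3 percentage points of extra error at ratio 1.25, with up to 12 points of lost power (66% − 54%), down to no error above nominal when within-subject CV is 30–40%.

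The change is worth making because it is cheap and fixes the estimand. The study's conclusions are not in serious danger: its main product is IVIVC data.

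**What to change.** Replace the normality and Box-Cox rule in section 7.3 with a pre-specified analysis:

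1. Analyse ln(Cmax), ln(AUC) and ln(clearance/uptake amount ratio) in a model with subject and product effects.
2. Report the between-product geometric mean ratio with a 90% confidence interval, judged against 80–125%.
3. Check the residuals of these log-scale models, not the distribution of concentrations.
4. Keep the within-subject permutation and bootstrap procedures as a sensitivity analysis of the log ratio.

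Make this change together with replacing the difference test by an equivalence test. On the log scale, a p<0.05 test of no difference still does not address a null hypothesis of lying "outside the 80–125% range". Conversely, adding an equivalence test alone would leave its scale to the data.

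The cost is SAP wording only. No new data are needed, and the analysis becomes slightly simpler.
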